11.1.4.2 Evaluation of Non-Target Lesions

Complete Response (CR): Disappearance of all non-target lesions, as assessed visually, for at least 4 weeks.

Non-CR/Non-PD: Persistence of one or more non-target lesion(s).

Progressive Disease (PD): Appearance of one or more new lesions and/or *unequivocal progression* of existing non-target lesions. *Unequivocal progression* should not normally trump target lesion status. It must be representative of overall disease status change, not a single lesion increase.

Although a clear progression of “non-target” lesions only is exceptional, the opinion of the treating physician should prevail in such circumstances, and the progression status should be confirmed at a later time by the review panel (or Principal Investigator).

11.1.4.3 Evaluation of New Lesions

The finding of a new lesion should be unequivocal. If a new lesion is equivocal (because of small size, etc.), follow-up evaluation will clarify if it truly represents new disease and if PD is confirmed, progression should be declared using the date of the initial documentation when the lesion was discovered.

11.1.4.4 Evaluation of Best Overall Response

The best overall response is the best response recorded from study registration until first disease progression/diagnosis of invasive OSCC (taking as reference for progressive disease the smallest measurements recorded since the treatment started). The patient's best response assignment will depend on the achievement of both measurement and histologic criteria.

Measurable Disease (*i.e.*, Target Disease)

Target Lesions	Non-Target Lesions	New Lesions	Overall Response	Best Overall Response when Confirmation is Required*
CR	CR	No	CR	≥ 4 wks Confirmation**
CR	Non-CR/Non-PD	No	PR	≥ 4 wks Confirmation**
CR	Not evaluated	No	PR	
PR	Non-CR/Non-PD/not	No	PR	

	evaluated				
SD	Non-CR/Non-PD/not evaluated	No	SD	Documented at least once \geq 4 weeks from baseline**	
PD	Any	Yes or No	PD	no prior SD, PR or CR	
Any	PD***	Yes or No	PD		
Any	Any	Yes	PD		

* See manuscript for further details on what is evidence of a new lesion.
 
** Only for non-randomized trials with response as primary endpoint.
 
*** In exceptional circumstances, unequivocal progression in non-target lesions may be accepted as disease progression.
					

Note: Participants with a global deterioration of health status requiring discontinuation of treatment without objective evidence of disease progression at that time should be reported as “symptomatic deterioration.” Every effort should be made to document the objective progression even after discontinuation of treatment.
					

Non-Measurable Disease (*i.e.*, Non-Target Disease)

Non-Target Lesions	New Lesions	Overall Response
CR	No	CR
Non-CR/non-PD	No	Non-CR/non-PD*
Not all evaluated	No	Not evaluated
Unequivocal PD	Yes or No	PD
Any	Yes	PD

* ‘Non-CR/non-PD’ is preferred over ‘stable disease’ for non-target disease since SD is increasingly used as an endpoint for assessment of efficacy in some trials so to assign this category when no lesions can be measured is not advised.

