5. TREATMENT PLAN

Treatment will be administered on an outpatient basis. No investigational or commercial agents or therapies other than nivolumab (BMS-936558) may be administered with the intent to treat the participant’s oral high-risk leukoplakia during the course of treatment.

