5.4.1 Prohibited and/or Restricted Treatments

The following medications are prohibited during the study (unless utilized to treat a drug related adverse event):

- Immunosuppressive agents
- Immunosuppressive doses of systemic corticosteroids
- Any anti-neoplastic therapy (i.e., chemotherapy, hormonal therapy, immunotherapy, extensive, non-palliative radiation therapy, or standard or investigational agents for treatment of NSCLC)

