5.4.3 Permitted Therapy

Participants are permitted the use of topical, ocular, intra-articular, intranasal, and inhalational corticosteroids (with minimal systemic absorption). Adrenal replacement steroid doses \leq 20 mg daily prednisone are permitted. A brief (less than 3 weeks) course of corticosteroids for

prophylaxis (e.g., contrast dye allergy) or for treatment of non-autoimmune conditions (e.g., delayed-type hypersensitivity reaction caused by a contact allergen) is permitted.

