5.5 Criteria for Taking a Participant Off Protocol Therapy

Adverse events will be continuously monitored throughout the trial by the study team with decisions made accordingly regarding the study status and patient entry throughout the duration of the trial.

Any adverse event(s) attributed to the study medication should result in a delay in future dosing. Therapy can be resumed at the discretion of the treating physician or PI. Duration of therapy will depend on individual tolerance and response. In the absence of treatment delays due to adverse event(s), treatment may continue for four cycles or until one of the following criteria applies:

- A diagnosis of invasive squamous cell carcinoma of the head and neck is confirmed at any point during study screening or on study. Note: if pre-treatment target lesions are increasing in size during the study period then the patient is permitted to continue with treatment until formal response assessment after the four planned doses of nivolumab. However, it is at the discretion of the treating physician whether to re-biopsy any target site before completion of the four planned doses of study treatment. If the patient develops a new measurable site during the treatment period, the patient can receive the four planned doses of treatment if an on-study biopsy of the new site confirms dysplasia without carcinoma in situ or invasive squamous cell carcinoma. A diagnosis of invasive squamous cell carcinoma at any point during the study warrants referral to a head & neck surgeon for consideration of oncologic resection.
- Intercurrent illness that prevents further administration of treatment
- Unacceptable adverse event(s)
- Participant demonstrates an inability or unwillingness to comply with the medication regimen and/or documentation requirements
- Participant decides to withdraw from the protocol therapy
- General or specific changes in the participant's condition render the participant unacceptable for further treatment in the judgment of the treating investigator

Participants will be removed from the protocol therapy when any of these criteria apply. The reason for removal from protocol therapy, and the date the participant was removed, must be documented in the case report form (CRF). Alternative care options will be discussed with the participant.

When a participant is removed from protocol therapy and/or is off of the study, the relevant Off-Treatment/Off-Study information will be updated in OnCore.

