5.6 Duration of Follow-Up

Participants, regardless if they receive the full course of therapy, will be followed for best overall response and development of first invasive OSCC and for survival for 5 years from the time of study registration throughout the course of the trial. Participants removed from protocol therapy for unacceptable adverse event and if they have not developed first invasive OSCC at time of discontinuation of protocol therapy, will continue to be followed until first invasive OSCC and survival until death or 5 years from study registration (whichever occurs first).

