- f) Baseline biopsy can be performed any time after the subject has consented up until C1D1. Archival tissue is not acceptable. Fresh biopsy is mandatory (at up to three sites per patient). Fresh tissue is also collected following completion of treatment. Biopsy will also be recommended if the patient progresses to invasive squamous cell carcinoma of the head and neck. Fresh tissue may also be collected at time of progression.
- g) Quality of life surveys will be completed at screening, after 2 cycles of treatment, at the end of treatment, and at 30-day follow-up. Patients will complete the chronic oral mucosal diseases quality of life questionnaire (COMD QLQ [66]). This is a validated instrument that assesses various aspects of oral health and function that has been shown to perform well in patients with oral mucosal diseases, including oral precancerous conditions. *See Appendix C* for the full questionnaire.
- h) Participants, regardless if they receive the full course of prescribed therapy, will be followed for best overall response and development of first invasive OSCC every cycle during treatment (including a survival status update). Post end-of-protocol treatment, if first invasive OSCC has not been confirmed, assessments will continue every 3-6 months until best overall response and first invasive OSCC are documented (with survival status updates during this time period as well). After documentation of first invasive OSCC, survival status will continue to be updated every 3 months until death or 5 years from study registration (whichever occurs first). Photographs and measurements may continue at PI discretion after first invasive OSCC and during survival follow up. Clinically indicated biopsies that occur at or following first invasive OSCC can be used for study correlatives at PI discretion during survival follow up.

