11. MEASUREMENT OF EFFECT

11.1 Measurement of Effect – OPVL lesions

For the purposes of this study, participants will be re-evaluated for change in the measurements of each oral leukoplakia site at every study visit following initial study drug dosing. In addition, re-biopsy of initial oral leukoplakia sites (up to 3 per patient) will be obtained at the end of treatment, and to development of invasive oral cancer up to 5 years from study registration. Timelines are described in *Section 10*.

Response will be measured by: (1) measuring the change in size of each oral leukoplakia lesion,

and (2) by assessing histopathological change (a change in the degree of dysplasia as defined by histologic features) [modified from Wan der Waal I, et al. *Oral Oncol* 2000; 36(3):264-6]. *See Response Criteria below.*

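### The best-overall-response window stays open after non-protocol local treatment of a lesion, so a later fall in score would count as response to nivolumab

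*Combined protocol and SAP*

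**What the plan says.** **The window.** Section 11.1.4.4 takes the "best response recorded from study registration until first disease progression/diagnosis of invasive OSCC". It names no other closing event.

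**How long scoring continues.** Under Section 5.6, participants "will be followed for best overall response and development of first invasive OSCC and for survival for 5 years" from registration. Footnote h of the Study Calendar (Section 10) says that after treatment, if invasive OSCC has not been confirmed, "assessments will continue every 3-6 months until best overall response and first invasive OSCC are documented". Section 11.1 extends re-biopsy of the initial sites beyond the end of treatment, "and to development of invasive oral cancer up to 5 years from study registration". The calendar marks photographs, measurements and biopsies in the survival follow-up column as well as at the 30-day visit.

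**What other treatment is barred.** Section 5 bars other agents or therapies intended to treat the "oral high-risk leukoplakia during the course of treatment", which is at most four 28-day cycles (Section 5.2). Section 5.4.1 is a list of medications prohibited during the study. It includes "Any anti-neoplastic therapy (i.e., chemotherapy, hormonal therapy, immunotherapy" and further items, but does not name excision, laser or photodynamic treatment.

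**What the documents expect in this disease.** Section 2.1 calls surgery the most used treatment, and Section 2.3 lists excision, laser and photodynamic therapy among current strategies. Section 11.1.7 foresees resection for CIS. CIS is neither a histology grade in Section 11.1.4.1 nor an event that closes the response window.

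**The decision rule.** Section 13 requires more than 5 responders among 33, after more than 1 among the first 16.

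**The concern.** The primary endpoint of this single-arm trial is meant to measure response to nivolumab. A best-response rule keeps the most favourable assessment in the window. If a lesion is cut back or ablated after the treatment course, and progression has not been declared, the next assessment can be better than the post-treatment one and replace it. Nothing in the off-therapy and off-study criteria (5.5, 5.7), the response rules (11.1.4), the duration-of-response definition (11.1.5) or Section 13 says that such an assessment should be set aside.

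Under a best-response rule, the error can only add responders. There is no control arm in which it would cancel, and the final cut-off is low in absolute terms: one responder is 1/33 = 3.0 percentage points.

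**Working it through.** **1. The plan's own figures.** Inputs from Section 13: n1 = 16, stop if at most 1 response; n = 33, success if at least 6. With X1 ~ Bin(16, p) and X2 ~ Bin(17, p):

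- P(stop early) = P(X1 ≤ 1)
- P(success) = P(X1 ≥ 2 and X1 + X2 ≥ 6)

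| True rate | P(stop early) | P(success) | Stated |
|---|---|---|---|
| 10% | 51.5% | 9.8% | 51.5%, 9.8% |
| 25% | 6.3% | 84.3% | 84.3% (success) |

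The stated figures reproduce.

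**2. Can local treatment produce a response on the grid?** Using the points in Section 11.1.4.1, for a single target lesion at L3P2 = 26:

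- Residual or recurrent lesion at L2P1 = 14: (26 − 14)/26 = 46.2%, in the PR range.
- Residual or recurrent lesion at L1P1 = 4: (26 − 4)/26 = 84.6%, in the CR range if sustained for 4 weeks.

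Both follow-up scores are ordinary grid cells, so no scoring assumption is needed. A fully excised site is different. The grid has no value for an absent lesion, so any score given to it is an assumption.

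**3. Does progression close the window first?** Sometimes. Section 11.1.4.1 sets PD at an increase of 10% or more. For a single lesion, with baseline as the reference:

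- One-grade worsening from L2P0, L2P1 or L2P2: 2/12 = 16.7%, 2/14 = 14.3%, 2/16 = 12.5%. All are PD, so the window closes. L1 lesions rise by at least 2/6 = 33.3%, also PD.
- One-grade worsening from L3P0, L3P1 or L3P2: 2/22 = 9.1%, 2/24 = 8.3%, 2/26 = 7.7%. All are below 10%, so the window stays open.
- CIS, if scored at least as P3 (an assumption, since it is not graded): from L3P0, 6/22 = 27.3%; from L3P1, 4/24 = 16.7%. Both are PD. From L3P2, 2/26 = 7.7%, not PD.

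Local treatment also need not follow any worsening, and then nothing closes the window.

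**4. Illustrative effect on the decision.** Assume a true rate of 10%, stage 1 judged on genuine responses only, and each genuine non-responder misattributed with probability f by the final analysis. Let T be the genuine total, with stage 1 passed. Then P(declare activity) = Σ P(T = t, X1 ≥ 2) × P(t + Bin(33 − t, f) ≥ 6). The documents give no value for f.

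| Assumed f | P(declare activity) |
|---|---|
| 0 | 9.8% |
| 1% | 12.8% |
| 2% | 15.9% |
| 5% | 25.5% |

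**5. Fixed numbers of misattributed patients.** If exactly one misattributed responder were certain, the probability is P(X1 ≥ 2, T ≥ 5) = 19.9%. If two were certain, it is P(X1 ≥ 2, T ≥ 4) = 32.9%. These are conditional figures, not estimates of the trial's error rate.

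**The case against.** **The main assessment comes early.** Section 5.5 refers to a "formal response assessment after the four planned doses of nivolumab", and the calendar places biopsy and measurements at the 30-day visit. Until the end of the treatment course, Section 5 bars other therapies for the leukoplakia. This stands as a limit on exposure, which is mainly after the 30-day visit. It does not close the gap, because 11.1.4.4 does not restrict best response to that assessment and 5.6 continues follow-up for it.

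**Both size and histology are needed.** Section 11.1.4.4 makes best response depend on both, and a fully excised site has neither. This also stands. A reader might infer that excising Patient B's lesion yields a complete response: a fall of 24/26 = 92.3% if the absent lesion scores 2, or 26/26 = 100% if it scores 0. The documents do not support that. Two points denote a lesion still present at L1P0, zero is not on the grid, and not evaluable is at least as natural a reading. The route that needs no assumption is a site that still has, or again has, a lesion and is re-biopsied. No fixed schedule for late re-biopsy is given, although Section 11.1 allows it.

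**Progression often comes first.** Step 3 shows this for L1 and L2 lesions and for CIS arising from L3P0 or L3P1 if graded as P3. New lesions are also PD. That narrows the route without removing it.

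**Some patients are less likely to have surgery.** Eligibility groups 3 and 4 enter with surgery indicated but not feasible or refused. This may lower the frequency in those groups, but no figure is given.

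**Conclusion.** The point holds as a gap in the endpoint definition. As written, the rule credits to nivolumab any fall in score seen after later non-protocol local treatment, provided that neither progression nor invasive OSCC has been recorded. The bias is one-directional and bears on the primary endpoint.

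Its size cannot be estimated from the documents, because they give no rate of such treatment. The range of 12.8% to 25.5% rests on assumed misattribution of 1% to 5% of non-responders, a true rate of 10%, and an unaffected first stage. A reader might infer from step 5 that the trial's false-positive probability is really 19.9% or 32.9%. That would require one or two misattributed responders to be certain in every trial, which nothing in the plan indicates. The stated 9.8% is correct for the design as specified.

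This is a cheap improvement worth making, not a flaw in the sample size calculation.

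**What to change.** State in Sections 11.1.4.4 and 13:

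> Best overall response uses only assessments made before the earliest of first progression, diagnosis of invasive OSCC, or first non-protocol treatment given with intent to treat the leukoplakia or a lesion (surgery, laser, photodynamic or drug therapy). Diagnostic biopsies and the medications permitted in Section 5.4.3 do not close the window. Patients who receive such treatment remain in the denominator with their best earlier response.

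Record the date and site of the treatment on the CRF, and report later assessments separately. This defines which assessments count and leaves clinical management as it is.

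**Cost.** A few sentences in two sections and one short CRF entry, with no extra visit and no change of endpoint. The downside is that a genuine late response appearing after local treatment is not counted.

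**Not covered.** The missing grid value for an absent lesion is a separate matter in Section 11.1.4.1. So is Patient A's printed total of 38, where the grid gives 4 + 14 + 18 = 36. This wording resolves neither.

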11.1.5 Duration of Response

Duration of overall response: The duration of overall response is measured from the time measurement criteria are met for CR or PR (whichever is first recorded) until the first date that recurrent or progressive disease is objectively documented (taking as reference for progressive disease the smallest measurements recorded since the treatment started, or death due to any cause. Participants without events reported are censored at the last disease evaluation).

Duration of overall complete response: The duration of overall CR is measured from the time measurement criteria are first met for CR until the first date that progressive disease is objectively documented, or death due to any cause. Participants without events reported are censored at the last disease evaluation.

Duration of stable disease: Stable disease is measured from the start of the treatment until the criteria for progression are met, taking as reference the smallest measurements recorded since the treatment started, including the baseline measurements.

11.1.6 Cancer-Free Survival and Overall Survival

Overall Survival: Overall Survival (OS) is defined as the time from study registration to death due to any cause, or censored at date last known alive.

Cancer-Free Survival: Cancer-Free Survival (DFS) is defined as the time from study registration to development of invasive oral cancer or death due to any cause. Participants alive without disease progression or recurrence (of invasive oral cancer) are censored at date of last disease evaluation.

11.1.7 Time to Next Surgery

Time to Next Surgery: Time to Next Surgery is defined as the time from the first study treatment to any head & neck surgery or resection for biopsy-proven carcinoma in situ (CIS) or invasive oral carcinoma (including all stages).

11.1.8 Quality of life Assessment

Quality of Life Assessment: The chronic oral mucosal diseases quality of life questionnaire (COMD QLQ, *see Appendix C*) will be used to assess the effect of the participants mouth condition on daily life activities. The survey consists of 24 questions with five response options per item. The response for each item is coded from 0 to 4 with “not at all = 0” and “extremely = 4” (at time of scoring, for 3 questions, the likert scale is reversed). The summary of the overall score ranges from 0 to 104, with a higher score indicating a poorer patient-assessed quality of life score.

12. DATA REPORTING / REGULATORY REQUIREMENTS

Adverse event lists, guidelines, and instructions for AE reporting can be found in Section 7.0 (Adverse Events: List and Reporting Requirements).

12.1 Data Reporting

12.1.1 Method

The Office of Data Quality (ODQ) will collect, manage, and perform quality checks on the data for this study.

12.1.2 Responsibility for Data Submission

Study team is responsible for entering data in the eDC system (InForm), within the timeframe, in accordance with DF/HCC SOPs.

12.2 Data Safety Monitoring

The DF/HCC Data and Safety Monitoring Committee (DSMC) will review and monitor toxicity and accrual data from this study. The committee is composed of clinical specialists with experience in oncology and who have no direct relationship with the study. Information that

raises any questions about participant safety will be addressed with the Overall PI and study team.

The DSMC will review each protocol up to four times a year or more often if required to review toxicity and accrual data. Information to be provided to the committee may include: up-to-date participant accrual; current dose level information; DLT information; all grade 2 or higher unexpected adverse events that have been reported; summary of all deaths occurring within 30 days of intervention for Phase I or II protocols; for gene therapy protocols, summary of all deaths while being treated and during active follow-up; any response information; audit results, and a summary provided by the study team. Other information (e.g. scans, laboratory values) will be provided upon request.

13. STATISTICAL CONSIDERATIONS

The primary objective of this trial is to evaluate best overall response rate (CR+PR). A two-stage design (Simon's optimal design) will be used to minimize the number of patients enrolled. Sixteen eligible patients who start protocol treatment are to be accrued in the first stage. If there are ≤ 1 patients with disease in response, accrual to this trial will be closed with the expectation that there is little evidence that the response rate will reach 25%. The probability that the trial will close early is 51.5% if the true response rate is 10%. If there are >1 patients with disease in response, accrual will continue until a total of 33 eligible patients who start protocol treatment are entered. If there are > 5 patients with disease in response among 33 eligible patients who began protocol treatment, further testing of this regimen will be considered. If the true response rate is 25%, the probability of concluding the regimen is effective is 84.3%, if the true response rate is 10%, the probability of concluding the regimen is effective is 9.8%. Allowing for patients to be declared ineligible or to not start protocol treatment after registration, a total of 35 patients will be entered.

The primary efficacy population includes all eligible patients who begin protocol treatment. Best overall response will be summarized as a proportion with a corresponding exact 95% confidence interval (CI) (if the trial closes to accrual after the first stage), or a corresponding 95% (two-stage) CI if the trial closes to accrual after the second stage.

For secondary objectives:

- Adverse events will be classified and graded according to the CTCAE v.5.0. Frequencies of adverse events will be summarized among patients who begin protocol therapy. The following stopping rule will be used to monitor excessive protocol related toxicity: if 3 or more of the first 10 patients who begin protocol treatment experience treatment related toxicities which cause extreme delays (protocol treatment needed to be stopped >10 weeks) or excessive treatment related toxicities, accrual to the trial will be suspended to further evaluate the events and decisions made regarding the overall status of the trial. If the true rate due to toxicity is 10% then the probability of suspending accrual is 7%; if the true rate is 20%, then the probability of suspending accrual is 32%; if the true delay rate is 30% then the probability of suspending accrual is 62%. Adverse events will be continuously monitored throughout the trial by the study team with decisions made accordingly regarding the study status and patient entry throughout the duration of the trial.

- The distributions of time-to-event endpoints will be estimated using the Kaplan-Meier method with corresponding 95% confidence intervals for the median or time-specific event time.
- Another endpoint is to assess quality of life (QOL). QOL will be assessed via self-report questionnaires at the timepoints outlined in the Study Calendar. Descriptive statistics from the questionnaires will be summarized across timepoints of assessment. Rates of drop-out/non-response to QOL assessments and corresponding reason will also be summarized across timepoints of assessment.
- Several correlative studies are also planned. Given the small sample size of this trial, these studies are exploratory. Samples will be collected at baseline and at post-baseline timepoints as outlined in the Study Calendar. Human immune cell markers (see 9.1 Biomarker Studies) from patients with evaluable tumor and peripheral blood samples will be summarized descriptively and graphically. Within subject changes in these markers will also be analyzed. Correlation between immune checkpoint receptor ligands and best overall response will be analyzed. Assuming 27 evaluable patients with baseline and a post-baseline value provides 80% power to detect .58 SD mean difference (Wilcoxon sign rank test two-sided 0.05 alpha level) in any given circulating or tumor immune marker.

With an estimated monthly accrual of 3 patients, the first stage is estimated to complete accrual in approximately 6 months. Due to possible delays in initiation of approval and/or in initiation of accrual itself, accrual to the first stage could take longer. As is customary with this type of design, accrual will be suspended after the first stage (n = 16 eligible patients who begin protocol therapy) in order to assess outcome; however, this suspension is also dependent on the actual observed accrual rate and the number of patients with confirmation of disease response status while the first stage of the trial is accruing.

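### Section 13 sets no numeric toxicity boundary after the tenth treated patient; one cumulative look while accrual is open would extend the rule at little cost

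*Combined protocol and SAP*

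**What the plan says.** Section 13 (Statistical Considerations), in the adverse-event item under the secondary objectives, calls for action "if 3 or more of the first 10 patients who begin protocol treatment experience treatment related toxicities which cause extreme delays". Extreme means that protocol treatment had to stop for more than 10 weeks. A second event type follows: "or excessive treatment related toxicities, accrual to the trial will be suspended to further evaluate the events". Section 13 tabulates suspension probabilities of 7%, 32% and 62% at true rates of 10%, 20% and 30%.

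Section 6 (Dosing Delays/Dose Modifications) promises a safety run-in for the initial participants, because use in the oral precancerous setting is relatively new, and refers to Section 13 for the details. The 3-of-10 rule is the only candidate there.

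For everyone, including patients after the tenth, Section 13 adds: "Adverse events will be continuously monitored throughout the trial by the study team with decisions made accordingly". Section 5.5 says the same. Section 12.2 has the DSMC review toxicity and accrual up to four times a year, or more often if needed. None of these provisions carries a threshold.

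On size, Section 13 says: "Sixteen eligible patients who start protocol treatment are to be accrued in the first stage". If stage 2 opens, "accrual will continue until a total of 33 eligible patients who start protocol treatment are entered". Up to 35 may be registered.

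**The concern.** Section 13 presents the 3-of-10 rule as the stopping rule for excessive toxicity, yet it uses only the first 10 of as many as 33 patients. If two of those ten have an event, the rule is passed, and later events count toward no predefined limit. At a true rate of 30%, about 23 × 0.30 = 6.9 events would be expected among the remaining 23 patients without any number in the plan calling for a pause.

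Section 7.4 already requires adverse events to be recorded for every patient, so the information for a later count would exist. What is at stake is whether the study team and the DSMC have an agreed trigger, with known operating characteristics, for the larger part of the treated population.

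**Working it through.** **Inputs, all from Section 13.** Boundary: 3 or more events in 10 treated patients. Tabulated true rates: p = 0.10, 0.20, 0.30. Stage 1: 16 eligible treated patients. Both stages: 33. Maximum entered: 35.

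**1. Reproduce the plan's figures.** P(suspend) = 1 − Σ C(10,x) pˣ (1−p)^(10−x), summed over x = 0, 1, 2.

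- p = 0.10: 1 − (0.3487 + 0.3874 + 0.1937) = 0.0702
- p = 0.20: 1 − (0.1074 + 0.2684 + 0.3020) = 0.3222
- p = 0.30: 1 − (0.0282 + 0.1211 + 0.2335) = 0.6172

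These agree with 7%, 32% and 62%. The chance of not crossing the rule at p = 0.30 is 1 − 0.6172 = 0.3828, or 38%. This is a property of a 10-patient look; it does not arise from the absence of later looks.

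**2. Patients after the boundary.** 33 − 10 = 23 if both stages accrue; 16 − 10 = 6 if the trial closes after stage 1; 35 − 10 = 25 if every registered patient starts treatment.

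**3. Add one cumulative look.** With a boundary of b events at patient n, and Y binomial with n − 10 trials:

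P(suspend) = P(X₁₀ ≥ 3) + Σ P(X₁₀ = x) × P(Y ≥ b − x), summed over x = 0, 1, 2.

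For 5 of 20 at p = 0.30, the sum is 0.0282 × 0.1503 + 0.1211 × 0.3504 + 0.2335 × 0.6172 = 0.1908, so the total is 0.6172 + 0.1908 = 0.8080. At p = 0.20 the total is 0.32220 + 0.13327 = 0.45547, and at p = 0.10 it is 0.0702 + 0.0191 = 0.0893.

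For 4 of 16, the added terms are 0.0287, 0.1324 and 0.1683 at p = 0.10, 0.20 and 0.30.

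| Rule | 10% | 20% | 30% |
|---|---|---|---|
| 3/10 (plan) | 7.0% | 32.2% | 61.7% |
| 3/10 and 5/20 | 8.9% | 45.5% | 80.8% |
| 3/10 and 4/16 | 9.9% | 45.5% | 78.6% |
| 3/10 and 6/20 | 7.3% | 36.8% | 71.9% |

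The last row shows how far the gain depends on the chosen threshold. At a 30% rate, the chance of not crossing falls from 38% to 19% with 5 of 20, and to 21% with 4 of 16.

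**4. A look at patient 33.** Adding 8 of 33 to 3/10 and 5/20 gives 9.3%, 51.7% and 88.9%, an apparent further gain of 0.4, 6.2 and 8.1 points. Planned accrual of eligible treated patients is complete at that look, so these points cannot be counted as suspensions of accrual.

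**The case against.** The strongest reply is that the rule does what Section 6 announces. It is a run-in for the initial participants, and Section 13 reports its operating characteristics correctly. Monitoring does not end at patient 10: the study team may change study status or patient entry at any time, the DSMC reviews toxicity independently, Section 6 sets individual delay and discontinuation criteria, and accrual is normally to pause after 16 patients. Nothing in the documents is contradicted. All of this stands. What remains is that none of these mechanisms has a threshold, and that the run-in rule is also the only quantitative toxicity rule in the plan.

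A reader might infer that a 30% rate goes unaddressed 38% of the time, or that events after patient 10 trigger nothing. The documents support neither reading. The 38% is the chance of not crossing one numeric rule; judgement-based suspension remains available throughout.

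Three further points limit the size. The 23 patients require stage 2 to open; if the true response rate is 10%, the plan itself gives a 51.5% chance of closing at 16, and a 20-patient look would then never be reached. Section 13 tabulates 20% and 30% without calling either unacceptable, so extra pauses at 20% may be protection or nuisance. Finally, one event type takes more than 10 weeks to establish; at 3 patients a month, roughly 7 more could enter meanwhile, so the exact binomial figures flatter any look taken without waiting, including the plan's own.

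**Conclusion.** The point holds as a gap in the scope of a correctly calculated rule. There is no numeric boundary after the tenth treated patient, which leaves 23 patients (6 if the trial closes after stage 1, at most 25) under monitoring by judgement only. One added look while accrual is open would raise the chance of a predefined pause at a 30% rate from 61.7% to about 79–81% under the illustrative thresholds, and by less under a stricter threshold such as 6 of 20. It is an inexpensive safety improvement to a declared run-in, and does not correct an error in the plan.

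The figures assume independent patients with a common event rate, events known at each look, and a tabulated rate that covers both event types. The last assumption needs care: Section 13 does not define excessive toxicity, and its wording moves from a rate due to toxicity to a delay rate ("if the true delay rate is 30% then the probability of suspending accrual is 62" per cent).

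**What to change.** Keep the event definition and the 3-of-10 rule. Add at least one cumulative boundary at a patient number reached while accrual is still open, and tabulate the resulting suspension probabilities in Section 13 at the same three rates. A look at 16 could use the planned stage-1 pause and is reached even if stage 2 does not open; a look at 20 applies only in stage 2. Do not use a look at 33 as an accrual-suspension rule. State whether the tabulated rate covers both event types, and how patients whose events cannot yet be known are handled at each look. If the sponsor prefers no later boundary, Section 13 should say so and give the reason.

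The thresholds above are illustrations. Which rate is unacceptable is a clinical decision for the sponsor, and the thresholds should follow from it.

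The cost is a sentence and a small table, with no new data collection. The downside is more pauses: 1.9 points (5 of 20) or 2.9 points (4 of 16) at a 10% rate, and about 13 points at 20% with either. Crossing the boundary suspends accrual for evaluation; it does not by itself close the trial.
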